If [name] or [name] are notified of a patient at risk for suicidal behavior, [name] will contact that patient, verify their response and decide if a wellness check from police is needed or other interventions. That patient will be offered immediate assistance, including calling an

ambulance for transport to the Emergency Department, and their primary physician will be informed.

Randomization

Only Investigational Drug Services (IDS) Pharmacy will be aware of drug allocation prior to completion of data collection for the randomized, placebo-controlled study. A computer-generated randomization scheme will be used to randomize participants to receive either ketamine or saline (allocation ratio 1:1, blocks of 4). The study participants, intraoperative anesthesiologists, and study staff conducting postoperative assessments will be blinded to drug allocation until data collection is completed.

Infusions

The study intervention will occur during surgery (Study Day 0). Participants will be randomized to one of two groups: Group A (n=20) will receive a ketamine infusion of 0.5 mg/kg over 40 min during surgery, beginning after anesthetic induction with propofol. Group B (n=20) will receive a saline infusion over 40 min during surgery, beginning after anesthetic induction with propofol. Infusion (instead of bolus) dosing of ketamine was chosen since infusions have demonstrated antidepressant efficacy in outpatient psychiatric populations, as well as theoretically lower risk of adverse events due to lower peak serum concentrations compared to bolus dosing. A patient who is **not** enrolled in the study has a reasonable chance of receiving the same treatments (ketamine or saline) at comparable doses as those tested in the study.

Monitoring

Routine vital signs will be collected before and after surgery by the participant's nurse and reviewed by investigators. Each participant will have continuous physiological monitoring during their anesthetic. A SedLine® Brain Function Monitor will be used to evaluate depth of anesthesia/sedation. If the participant experiences an adverse event temporally related to the infusion where corrective action by the intraoperative anesthesiologist requires unblinding, then the study infusion drug will be revealed to the anesthesiologist.

Data Collection Procedures

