- Adverse Events Review
- Montgomery-Asberg Depression Rating Scale (MADRS)

By the Participant, reviewed by Investigators:

- Hospital Anxiety and Depression Scale (HADS)
- Brief Pain Inventory (BPI)

Day 7 (inpatient or via phone):

By Physician or Study Staff:

- Vital Signs (inpatient only)
- Concomitant Medication Review
- Adverse Events Review
- Montgomery-Asberg Depression Rating Scale (MADRS)

By the Participant, reviewed by Investigators:

- Hospital Anxiety and Depression Scale (HADS)
- Brief Pain Inventory (BPI)

Day 14 (inpatient or via phone):

By Physician or Study Staff:

- Ask participants what treatment they believe they received
- Reveal treatment to participant
- Vital Signs (inpatient only)
- Concomitant Medication Review
- Adverse Events Review
- Montgomery-Asberg Depression Rating Scale (MADRS)

By the Participant, reviewed by Investigators:

- Hospital Anxiety and Depression Scale (HADS)
- Brief Pain Inventory (BPI)

Participant Compensation:

• \$50 after completion of all study assessments

Study Procedures Matrix

	Screen- ing	Day 0 (Baseline)	Day 0 (Intraop)	Day 1	Day 2	Day 3	Day 5	Day 7	Day 14
PHQ-8	Х								
Inclusion/Exclusion Criteria	Х								
Demographic data	Х								
Consent	Х								
Concomitant Medication Review	X	Х		Х	Х	Х	X	Х	х
Medical and Psychiatric History	X								
Physical Exam	Х								
Vital Signs	X	Х		Х	Х	0	0	0	0
Continuous physiological monitoring			Х						
Urine toxicology screen test	Х								
Labs and studies as warranted by standard preoperative medical clearance (includes pregnancy test)	Х								
Mini International Neuropsychiatric Interview (MINI) - A , I & J	х								

Hospital Anxiety and Depression Scale (HADS)	×	x		x	x	x	X	х	х
Montgomery Asberg Depression Rating Scale (MADRS)	X	Х		X	X	X	X	X	х
Columbia Suicide Severity Rating Scale (CSSRS) – Short Screen	x								
Maudsley Staging Method (MSM)	Х								
Brief Pain Inventory	Х	Х		Х	Х	Х	Х	Х	Х
Randomization	Х								
Ketamine infusion or Placebo (saline) infusion			×						
SedLine® Brain Function Monitor			Х						
Ask participants what treatment they believe they received									Х
Treatment revealed to participant									Х
Participant compensation	X								х

X – required

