This is a single-site phase IV randomized clinical trial utilizing a quadruple-masked, placebo-controlled, parallel arm design. Participants will be randomly allocated in a 1:1 ratio to one of two groups: Group A (n=20) will receive a ketamine infusion of 0.5 mg/kg over 40 min during surgery. Group B (n=20) will receive a saline infusion over 40 min during surgery. In both groups, the study drug will be given after anesthetic induction. The participants, care providers, investigators, and outcomes assessors will be masked.

10. Randomization

Participants will be sequentially randomized as they enter the study. We will employ block randomization with 5 blocks of 8 patients each.

11. Sample size

We will enroll a total of 40 participants. Our sample size calculation was derived from an *a priori* power analysis for the primary outcome measure with a 1:1 allocation ratio. In a randomized controlled trial of ketamine vs active placebo (midazolam) performed by

Phillips et al. (2019), participants had a mean decrease of 10.9 points (SD=8.9) in MADRS total score relative to pre-infusion scores compared with a mean decrease of 2.8 points (SD=3.6) with midazolam. Using these results, we computed an estimated total sample size of 38 participants at a two-sided alpha level of 0.05 and 80% power. An additional 2 participants were added to account for potential attrition, for a total of 40 participants. Given the increased statistical efficiency of mixed models for repeated measures (MMRM) compared to parametric pre-post tests, we assumed that 40 participants should be sufficient to power our study for MMRM analysis.

12. Framework

We plan to evaluate the antidepressant superiority of ketamine to placebo by assessing the postoperative MADRS scores from postoperative Day 1 through Day 3. Additional outcomes collected at postoperative Day 5, 7, and 14 will be used for statistical model building and exploratory analyses.

13. Interim data monitoring

13a. Statistical interim analyses planned and time points

No statistical interim analyses planned.

13b. Any planned adjustment of significance level due to interim analysis

N/A.

13c. Details of guidance for stopping the trial early

N/A.

14. Timing of final analysis

Once all data have been collected at all planned time points from the final (40th) participant, all investigators will be unmasked and all outcomes will be analyzed together in the final analysis.

15. Timing of outcome assessments

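### Staff reveal treatment at each participant's own Day 14 visit, although the protocol leaves allocation with the pharmacy until the randomized study's data collection is complete, and no rule puts the Day 14 scales before the reveal

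*Protocol*

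**What the plan says.** **The reveal.** Protocol 8D, Data Collection Procedures, Day 14, lists "Reveal treatment to participant" among the tasks of the physician or study staff. The Study Procedures Matrix marks "Treatment revealed to participant" as required in the Day 14 column.

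**The blind in the protocol.** Protocol 8D, Randomization, states: "Only Investigational Drug Services (IDS) Pharmacy will be aware of drug allocation prior to completion of data collection for the randomized, placebo-controlled study". It adds that participants, intraoperative anesthesiologists and "study staff conducting postoperative assessments will be blinded to drug allocation until data collection is completed". The one exception, under Monitoring, is disclosure to the anesthesiologist when an adverse event requires it.

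**The blind in the SAP.** SAP 9: "The participants, care providers, investigators, and outcomes assessors will be masked". SAP 14 places unmasking after all time points are in "from the final (40th) participant, all investigators will be unmasked and all outcomes will be analyzed together in the final analysis". SAP 19c gives unblinding as an example of an emergency deviation.

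**Block size.** Protocol: "allocation ratio 1:1, blocks of 4". SAP 10: "We will employ block randomization with 5 blocks of 8 patients each".

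**Use of Day 14 data.** Remission is a main secondary outcome (SAP 26b), defined by a Day 14 MADRS of 12 or less. Day 14 HADS, pain and opioid use are further secondary outcomes. SAP 12 also uses later data, including Day 14, to help build the model.

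**The concern.** Staff cannot reveal what only the pharmacy is supposed to know. A site that follows the visit schedule breaks the Randomization section, and a site that follows the Randomization section cannot carry out the visit schedule.

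Two things are at stake.

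- **Day 14 outcomes.** If the reveal comes before the scales, a clinician-rated depression score and several self-reports are collected with treatment known. Remission rests entirely on one of them.
- **Later participants.** Even if the reveal comes last, whoever makes it learns allocations one at a time, at a single site with a fixed block size, while others are still being enrolled and rated. Knowledge of past allocations makes the next one easier to guess. That weakens concealment and rater masking for the Day 1-3 primary scores of people not yet treated.

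**Working it through.** No figure in the plan depends on this point. The check sets the texts side by side and then sizes the consequences under stated assumptions.

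**1. The texts.** The pharmacy-only sentence in Protocol 8D names the randomized study as a whole, so it runs to the end of that study's data collection. The Day 14 item applies to each participant. For everyone but the last, the reveal precedes the end of data collection. SAP 14 agrees with the trial-level reading for investigators; it sets no rule on telling participants, so the protocol sentence carries that point. On order, the visit list prints the reveal above MADRS, HADS and BPI, and the matrix prints it below them. Neither layout claims to be chronological, and no sentence settles the matter.

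**2. Day 14 MADRS, if the reveal comes first.** Assumptions: 20 per arm, no true effect, two-sided 0.05, and a difference between arms created only by knowing treatment. The central SD of 8.9 is borrowed from SAP 11, where it is the SD of change in the ketamine arm of a cited trial, not of Day 14 scores. The t-test is the protocol's method for continuous secondary outcomes. Noncentrality = shift / (SD × √(2/20)), with 38 df. For 3 points: 3 / (8.9 × 0.3162) = 1.07, giving 18.0% rejection.

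| Shift | SD 6 | SD 8.9 | SD 12 |
|---|---|---|---|
| 2 | 17.7% | 10.7% | 8.1% |
| 3 | 33.8% | 18.0% | 12.0% |
| 4 | 53.8% | 28.3% | 17.7% |

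**3. Remission, 3-point shift, SD 8.9.** P(remission) = Φ((12.5 − mean)/8.9). For a mean of 18: Φ(−0.618) = 0.268; after the shift, Φ(−0.281) = 0.389. Rejection is by exact enumeration of the uncorrected chi-squared test, 20 per arm.

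| Assumed Day 14 mean | Remission, no shift → shifted | Rejection, no shift | Rejection, shifted |
|---|---|---|---|
| 14 | 43% → 57% | 4.5% | 11.9% |
| 18 | 27% → 39% | 5.2% | 13.3% |
| 22 | 14% → 23% | 4.9% | 11.0% |
| 26 | 6% → 12% | 2.0% | 6.7% |

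With a continuity correction the shifted rates fall to 6.3%, 6.6%, 4.9% and 0.9% (no shift: 1.8%, 2.1%, 1.1%, 0.1%).

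**4. Leakage, whatever the order.** All permuted 1:1 blocks were enumerated and averaged over positions, with the guesser choosing the arm that has more places left. For blocks of 4 with all earlier members known, the chance of a correct guess at positions 1 to 4 is 1/2, 2/3, 2/3 and 1, mean 0.708. Certainty occurs at position 3 one time in three and always at position 4: (1/3 + 1)/4 = 0.333.

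| Most recent members not yet revealed | Blocks of 4: correct (certain) | Blocks of 8: correct (certain) |
|---|---|---|
| 0 (worst case) | 71% (33%) | 67% (20%) |
| 1 | 58% (8.3%) | 60% (7.5%) |
| 2 | 54% (0%) | 58% (2.1%) |

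Chance is 50%. The documents give no accrual rate. As a rough guide only, if enrollment began near the SAP 1.0 date (10/21/2019, an assumption), 75% of 40 = 30 participants by 10/28/2021 is 738/30 ≈ 25 days apiece. That is longer than 14 days, so the worst case need not be rare.

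**5. Primary model, complete data.** Assume response times 0, 2 (Days 1-3 combined), 5, 7 and 14, with random intercept and slope.

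- Categorical time: a Day 14 shift moves the Day 1-3 contrast by 0.
- Linear time: mean time 28/5 = 5.6, sum of squares 117.2. Per point of Day 14 shift the slope moves (14 − 5.6)/117.2 = 0.0717 per day, and the Day 2 contrast moves 1/5 + 0.0717 × (2 − 5.6) = −0.058. For 3 points: 0.215 per day (3.0 points over 14 days) and −0.17 points.

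The SAP does not state how time is coded.

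**The case against.** The sentence that blinds participants and assessors has no trial-level qualifier. Read per participant, it fits a Day 14 reveal and even implies that the scales come first. SAP 14 governs investigators only, and SAP 9 gives no end date for masking. That reading is fair, but it does not rescue the pharmacy-only sentence, which names the study, and that sentence alone is enough for the conflict.

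The visit lists are grouped by who performs each task, so their order proves nothing. This stands: the defect is silence on order, not a prescribed wrong order.

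The person who reveals treatment might be separate from the raters, and exploiting leakage requires knowing block position and size. Also true, but no separation is written, and the reveal and the MADRS sit under the same staff heading.

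The strongest point is that the primary outcome covers Days 1-3, before the participant's own reveal, and that a Day 14 shift moves its contrast by at most 0.17 points in the models tried. The directly exposed outcomes are secondary, and the protocol calls those exploratory. This limits the harm to the primary analysis. It does not remove the exposure of remission or the leakage to later participants. The size of any shift is not known from the documents.

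**Conclusion.** The concern holds, and the text must be corrected. The Day 14 reveal contradicts the pharmacy-only rule and does not fit the SAP's masking and end-of-trial unmasking. The order of scales, treatment guess and reveal is nowhere stated.

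The direct damage is to Day 14 outcomes, and only if the reveal comes first. A 3-point shift would raise false rejection on the Day 14 MADRS to between 12% and 34% for SDs of 12 down to 6, and on remission (uncorrected test) to about 7% to 13%. Shifts, means and SDs are assumptions. The indirect damage is leakage: correct guesses range from 54% to 71%, depending on block size and on how many recent participants have not been told, provided staff know the block structure.

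The primary contrast is little affected by Day 14 scores themselves; its exposure runs mainly through later participants. Lost masking cannot be restored in analysis, so this needs a procedural correction.

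**What to change.** 1. Remove the reveal from the Day 14 visit list and the matrix. State in Protocol 8D and SAP 14 that participants are told only after the 40th participant's Day 14 data are collected and locked. The consent pages are not available here, so check any disclosure timing promised there.
2. If a per-participant reveal must stay, amend the pharmacy-only sentence and SAP 9 and 14 to match. Fix the order as all Day 14 scales, then the treatment guess, then disclosure, and have someone outside recruitment and rating, such as the pharmacy, make it.
3. For participants already told, record whether the reveal preceded the scales, and report Day 14 outcomes collected after it as unmasked. State in SAP 27a that time is categorical; with complete data this keeps Day 14 scores from moving the Day 1-3 contrast. The figures give little reason to drop those scores from the primary model.
4. Reconcile the block size (4 or 8).
5. A question for the sponsor, not a demonstrated defect: SAP 4c says the change to version 2.0 preceded unblinding. How many participants had been told individually by then, and did anyone deciding the endpoint change know allocations?

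The cost is wording in both documents and one recorded item. The downside is that participants wait longer to learn their treatment.

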9. SIGNIFICANCE

Major Depressive Disorder (MDD) is widely prevalent among patients preparing to have surgery, and is a known risk factor for complications after surgery, including wound infection, myocardial infarction and opioid use disorder. Ketamine has emerged as an effective, rapid-acting antidepressant therapy for patients with MDD, and may be a useful tool to prevent MDD-related morbidity in the perioperative period. Ketamine has been well studied for MDD in outpatient clinics where it is given as an infusion (0.5 mg/kg over 40 minutes) in awake patients.

O - inpatient only

Ketamine is often used as part of an anesthetic cocktail in sedated or anesthetized patients, but it is unknown whether ketamine has an antidepressant effect in this context. We will determine whether a ketamine infusion, compared to placebo (normal saline infusion), has an antidepressant effect when given during surgical anesthesia. If ketamine is an effective antidepressant in this population under anesthesia, its use could be incorporated into a set of interventions to minimize the perioperative complications associated with MDD.

STATISTICAL ANALYSIS PLAN

Official Title:

Intraoperative Ketamine Versus Saline in Depressed Patients
Undergoing Anesthesia for Non-cardiac Surgery

NCT Number: 03861988

Protocol last edited: 10/28/2021

Statistical Analysis Plan (SAP)

Section 1: Administrative Information

1. Title and trial registration

1a. Title

Intraoperative Ketamine Versus Saline in Depressed Patients Undergoing Anesthesia for Non-Cardiac Surgery

1b. Trial registration number

ClinicalTrials.gov Identifier NCT# 03861988

2. SAP version: 2.0

3. Protocol version: Stanford eProtocol ID 49114, last revision submitted 8/9/21

4. SAP revisions

4a. SAP revision history

10/21/2019 – version 1.0 (originally included in the study protocol)

10/28/2021 – version 2.0 (created a new, separate SAP document)

4b. Justification for each SAP revision

Version 1.0 to 2.0:

- 1) In our original protocol, recruitment was limited to patients with symptomatic depression presenting for hip and knee arthroplasty at Stanford. Patients undergoing this type of surgery have a predictable postoperative course, which guided our primary endpoint selection. We encountered significant difficulties recruiting patients during the COVID-19 pandemic. Therefore, we expanded eligibility criteria by including patients presenting for a wider variety of surgical procedures, which are described in our updated protocol. To account for the likely increased variability of postoperative recovery in this broader population, we updated our primary endpoint to include data from the first 3 days after surgery, instead of only a single day after surgery.
- 2) In our original protocol, the primary outcome measure was defined as the sum of scores from a clinician-administered scale and a self-report scale. During the recruitment phase of our trial, and prior to unblinding, we presented our analysis plan to a panel of statisticians in the Department of Biomedical Data Sciences at Stanford University. The panel recommended that we could improve the interpretability and reduce the variance in our primary outcome by only using one validated measure (rather than a composite score) as our primary outcome measure. Based on this recommendation, we updated our primary outcome measure to only include the clinician-administered scale (the Montgomery-Asberg Depression Rating Scale).

4c. Timing of SAP revisions

This revision (1.0 to 2.0) was made prior to data unblinding and prior to completion of data collection (75% of target enrollment).

5. Roles of SAP contributors

[name], Stanford University, Primary SAP author

[name], PhD, Stanford University, Chief investigator/clinical lead

6. Signatures

6a. Primary SAP author: 

6b. Chief investigator/clinical lead: 

Section 2: Introduction

7. Background and rationale

Major depressive disorder (MDD) is widely prevalent among patients preparing to have surgery, and is a known risk factor for complications after surgery, including wound infection, myocardial infarction and opioid use disorder. Ketamine has emerged as an effective, rapid-acting antidepressant therapy for patients with MDD, and may be a useful tool to prevent MDD-related morbidity in the perioperative period. Ketamine has been well studied for MDD in outpatient clinics where it is given as an infusion (0.5 mg/kg over 40 minutes) in awake patients. Ketamine is often used as part of anesthetic cocktail in sedated or anesthetized patients, but it is unknown whether ketamine has an antidepressant effect in this context. We will determine whether a ketamine infusion, compared to placebo (normal saline infusion), has an antidepressant effect when given during surgical anesthesia.

8. Objectives

We hope to discover whether ketamine has antidepressant efficacy in major depressive disorder (MDD) patients when given as an anesthetic adjunct. If ketamine is an effective antidepressant in this population under anesthesia, its use could be incorporated into a set of interventions to minimize the perioperative complications associated with MDD. While it is more efficient to deliver ketamine therapy intraoperatively, if this study finds that ketamine is ineffective in this setting, that result establishes a rationale to test treatment prior to the surgical encounter. We will also have gained important information on ketamine's antidepressant mechanism (e.g. it is blocked by other anesthetics, or it requires that the patient be conscious).

Section 3: Study Methods

9. Trial design

This is a single-site phase IV randomized clinical trial utilizing a quadruple-masked, placebo-controlled, parallel arm design. Participants will be randomly allocated in a 1:1 ratio to one of two groups: Group A (n=20) will receive a ketamine infusion of 0.5 mg/kg over 40 min during surgery. Group B (n=20) will receive a saline infusion over 40 min during surgery. In both groups, the study drug will be given after anesthetic induction. The participants, care providers, investigators, and outcomes assessors will be masked.

10. Randomization

Participants will be sequentially randomized as they enter the study. We will employ block randomization with 5 blocks of 8 patients each.

11. Sample size

We will enroll a total of 40 participants. Our sample size calculation was derived from an *a priori* power analysis for the primary outcome measure with a 1:1 allocation ratio. In a randomized controlled trial of ketamine vs active placebo (midazolam) performed by

Phillips et al. (2019), participants had a mean decrease of 10.9 points (SD=8.9) in MADRS total score relative to pre-infusion scores compared with a mean decrease of 2.8 points (SD=3.6) with midazolam. Using these results, we computed an estimated total sample size of 38 participants at a two-sided alpha level of 0.05 and 80% power. An additional 2 participants were added to account for potential attrition, for a total of 40 participants. Given the increased statistical efficiency of mixed models for repeated measures (MMRM) compared to parametric pre-post tests, we assumed that 40 participants should be sufficient to power our study for MMRM analysis.

12. Framework

We plan to evaluate the antidepressant superiority of ketamine to placebo by assessing the postoperative MADRS scores from postoperative Day 1 through Day 3. Additional outcomes collected at postoperative Day 5, 7, and 14 will be used for statistical model building and exploratory analyses.

13. Interim data monitoring

13a. Statistical interim analyses planned and time points

No statistical interim analyses planned.

13b. Any planned adjustment of significance level due to interim analysis

N/A.

13c. Details of guidance for stopping the trial early

N/A.

14. Timing of final analysis

Once all data have been collected at all planned time points from the final (40th) participant, all investigators will be unmasked and all outcomes will be analyzed together in the final analysis.

15. Timing of outcome assessments

All patients will have at least one baseline psychiatric assessment prior to Day 0. Repeat baseline assessment by questionnaire will occur on the morning of surgery prior to any preoperative medication being given. The study assessments will be performed at postoperative Day 1, Day 2, Day 3, Day 5, Day 7 and Day 14. Assessments will be performed either in hospital or by phone or video.

Section 4: Statistical Principles

16. Level of statistical significance

We will use an uncorrected two-sided alpha of 0.05 as a cutoff for statistical significance.

17. Adjustment for multiplicity and controlling type I error

The primary outcome (MADRS score) that is measured on postoperative Day 1, 2, and 3 will be combined and treated as a single timepoint in the mixed model, rather than separately testing each day for significance which can inflate type I error rate.

Postoperative Days 1, 2, and 3 were chosen due to previously published data showing that the antidepressant effect of ketamine persists up to 3 days after administration.

18. Confidence intervals to be reported

We will report 95% confidence intervals for the primary outcome.

19. Adherence and protocol deviations

19a. Adherence to protocol and how this is assessed

Adherence to protocol is defined as: 1) participant meets eligibility criteria prior to randomization; 2) all planned assessments are completed; and 3) the patient receives the complete dose of the blinded study drug intravenously over a course of 40 minutes, initiated after induction of anesthesia and completed before extubation or transfer to the post-anesthetic recovery area.

19b. How adherence to protocol will be presented

Adherence to protocol will be presented as a proportion.

19c. Protocol deviations

Emergency protocol deviations are defined as those occurring in an emergency situation where departure from the protocol (such as unblinding the study drug) is required immediately to protect the life or physical well-being of the participant.

Non-emergent deviations are defined as those that do not occur in an emergency situation. Examples potentially encountered in our study include, but are not limited to: 1) participant is randomized to a treatment intervention but does not meet eligibility criteria, 2) the anesthesiologist administered the study drug incorrectly or incompletely, 3) the participant inadvertently received the intervention meant for the other trial arm, 4) the participant was not available for assessment of the planned outcome either because of loss to follow-up or for another reason, 5) study staff were not available for assessment of the planned outcome either because of a personal emergency or another reason.

19d. Which protocol deviations will be summarized

All emergency and non-emergent protocol deviations will be summarized.

20. Analysis populations

As recommended by CONSORT guidelines for parallel group randomized controlled trials, intention-to-treat and per-protocol analyses (if needed) will be performed and reported for all planned outcomes to allow readers to interpret the effects of the intervention.

Section 5: Trial Population

21. Screening data

Screening data to be collected and reported in CONSORT flow diagram include:

Patient Health Questionnaire score

HADS-MADRS composite score

English-speaking status

Age

Body mass index

History of significant CNS disease or brain surgery

History of moderate to severe substance use disorder (except nicotine)

History of schizophrenia, schizoaffective disorder, or psychosis

Chronic high dose opioid use (>90 morphine milligram equivalents per day)

High suicide risk

Other reasons

22. Eligibility

22a. Inclusion criteria

A subject will be eligible for inclusion only if all of the following criteria are met:

1. Male or female, 18 to 80 years of age, inclusive, at screen.
2. Able to read, understand, and provide written, dated informed consent prior to screening. Participants will be deemed likely to comply with study protocol and communicate with study personnel about adverse events and other clinically important information.
3. PHQ-8 score ≥ 12 .
4. Diagnosed with Major Depressive Disorder (MDD), single or recurrent, and currently experiencing a Major Depressive Episode (MDE) of at least 4 weeks in duration, prior to screening, according to the criteria defined in the Diagnosis and Statistical Manual of Mental Disorders, Fifth Edition. The diagnosis of MDD will be made by a trained study staff member and supported by the Mini International Neuropsychiatric Interview - Module A.
5. Meet the threshold on the total combined HADS-MADRS score of ≥ 31 at both screening and day of surgery visits.
6. In sufficiently good health to proceed with planned surgery, as ascertained by a standard preoperative clinic evaluation which includes medical history, physical examination (PE), clinical laboratory evaluations, any indicated cardiac testing, and final clearance by the attending anesthesiologists on the day of surgery.
7. Body mass index between 17-40kg/m².

8. Concurrent psychotherapy will be allowed if the type (e.g., supportive, cognitive behavioral, insight-oriented, et al) and frequency (e.g., weekly or monthly) of the therapy has been stable for at least 4 weeks prior to screening and if the type and frequency of the therapy is expected to remain stable during the course of the subject's participation in the study.

9. Concurrent antidepressant therapy (e.g. SSRI or SNRI) and/or hypnotic therapy (e.g. zolpidem, zaleplon, melatonin, or trazodone) will be allowed if the therapy has been stable for at least 4 weeks prior to screening and if it is expected to remain stable during the course of the subject's participation in the study.

22b. Exclusion criteria

A potential participant will NOT be eligible for participation in this study if any of the following criteria are met:

1. Female that is pregnant or breastfeeding. These women would not be candidates for elective surgery under any circumstances, and therefore would be screened out from our study population at their routine preoperative evaluation. Women of childbearing potential are routinely screened for pregnancy at their preoperative visit by urine hCG testing if clinically indicated. We will not be including pregnant women from other surgical populations as well.

2. Total HADS-MADRS score of <31 at either the screening or day of surgery visits.

3. Current diagnosis of a Substance Use Disorder (SUD; Abuse or Dependence, as defined by DSM-V) rated "moderate" or "severe" per criteria of the Mini International Neuropsychiatric Interview – Module J (MINI-J), or Alcohol Use Disorder rated "moderate" or "severe" per MINI-I criteria. These patients are rarely candidates for elective surgery. The following categories of SUD will NOT be excluded: nicotine dependence; alcohol or substance use disorder rated "mild"; alcohol or substance use disorder of any severity in remission, either early (3-12 months) or sustained (>12 months) time frames.

4. History of schizophrenia or schizoaffective disorders, or any history of psychotic symptoms in the current or previous depressive episodes.

5. In the judgment of the investigator, the subject is at significant risk for suicidal behavior during the course of his/her participation in the study.

6. Has dementia, delirium, amnestic, or any other cognitive disorder.

7. Has a clinically significant abnormality on the screening physical examination that would otherwise preclude the patient from having surgery.

8. Participation in any clinical trial with an investigational drug or device that conflicts with this trial, within the past month or concurrent to study participation.
9. Lifetime history of surgical procedures involving the brain or meninges, encephalitis, meningitis, degenerative central nervous system disorder (e.g., Alzheimer's or Parkinson's Disease), epilepsy, mental retardation, or any other disease/procedure/accident/intervention associated with significant injury to or malfunction of the central nervous system (CNS), or a history of significant head trauma within the past two years.
10. Presents with any of the following lab abnormalities w/in the past 6 months:
 - a. Thyroid stimulating hormone (TSH) outside of the normal limits and clinically significant as determined by the investigator. Free thyroxine (T4) levels may be measured if TSH level is high. Subject will be excluded if T4 level is clinically significant.
 - b. Any other clinically significant abnormal laboratory result at the time of the screening exam.
11. History of hypothyroidism and has been on a stable dosage of thyroid replacement medication for less than six months prior to screening. (Subjects on a stable dosage of thyroid replacement medication for at least six months or more prior to screening are eligible for enrollment.)
12. History of hyperthyroidism which was treated (medically or surgically) less than six months prior to screening.
13. Any current or past history of any physical condition which in the investigator's opinion might put the subject at risk or interfere with study results interpretation.
14. Patients currently maintained on high dose opioids (>90 morphine equivalents per day) prior to surgery

23. Recruitment

Information to be collected and reported in CONSORT flow diagram include:

Patients with a history of depression screened
Excluded due to PHQ score < 12
Excluded due to other exclusion criteria
Declined to participate
Lost to follow-up during screening
Excluded after consent
Withdrew after consent prior to intervention
Participants consented

24. Withdrawal and follow-up

24a. The following withdrawal/lost to follow-up data will be recorded:

- Number of participants who withdraw or are lost to follow-up
- Timing of withdrawal or lost to follow-up
- Reasons of withdrawal or lost to follow-up

24b. The above withdrawal/lost to follow-up data will be presented as:

- Percentages (%) of participants who withdraw or are lost to follow-up
- Kaplan-Meier curves of withdrawal or lost to follow-up (if any)
- Reasons of withdrawal or lost to follow-up summarized in the Results section

25. Baseline patient characteristics

25a. List of baseline characteristics to be reported

- 1) Sex (n, %)
- 2) Age (years, mean and SD)
- 3) Body mass index (mean, SD)
- 4) Hispanic/Latino ethnicity (n, %)
- 5) Race
 - a. White (n, %)
 - b. Black/African American (n, %)
 - c. Asian (n, %)
 - d. Native Hawaiian/Pacific Islander (n, %)
 - e. Other (n, %)
 - f. Unknown (n, %)
- 6) Married (n, %)
- 7) Disabled (n, %)
- 8) Current smoker (n, %)
- 9) PHQ score at screening (points, mean and SD)
- 10) HADS at screening (points, mean and SD)
- 11) MADRS at screening (points, mean and SD)
- 12) HADS-MADRS composite score at screening (points, mean and SD)
- 13) Age at first MDD onset (years, mean and SD)
- 14) Duration of current episode (months, mean and SD)
- 15) Recurrent major depression (n, %)
- 16) Previous clinical ketamine exposure (n, %)
- 17) Previous recreational ketamine exposure (n, %)
- 18) Charlson Comorbidity Index (points, mean and SD)
- 19) Maudsley resistance stage (points, mean and SD)
- 20) Numerical pain score (points, mean and SD)
- 21) Pain interference from BPI (points, mean and SD)

25b. Preoperative psychoactive medications

- 1) Opioids (n, %)

- 2) MME/day, if on opioids (mean, SD)
- 3) Anticonvulsants (n, %)
- 4) Benzodiazepines (n, %)
- 5) Muscle relaxants (n, %)
- 6) Antidepressants (n, %)
- 7) Antipsychotics (n, %)
- 8) Lithium (n, %)
- 9) Prescription sleep medications (n, %)
- 10) Opioid antagonists (n, %)
- 11) Stimulants (n, %)

25c. Surgical characteristics

- 1) Type of surgery
 - a. ENT/OMF (n, %)
 - b. Thoracic (n, %)
 - c. Breast (n, %)
 - d. Plastic non-breast (n, %)
 - e. Spine (n, %)
 - f. Major joint (n, %)
 - g. Other orthopedic/limb (n, %)
 - h. Intraabdominal general surgery (n, %)
 - i. Urologic and gynecologic (n, %)
 - j. Vascular (n, %)
 - k. Transplant (n, %)
- 2) Type of anesthesia
 - a. General anesthesia (n, %)
 - b. Monitored anesthesia care (n, %)
- 3) Intraoperative nitrous oxide (n, %)
- 4) Intraoperative propofol infusion (n, %)
- 5) Intraoperative opioid infusion (n, %)
- 6) Length of surgery (hours, mean and SD)
- 7) Peripheral or neuraxial catheter placed (n, %)

Section 6: Analysis

26. Outcome definitions

26a. Primary outcome

Postoperative MADRS scores from postoperative Days 1 through 3.

26b. Main secondary outcomes

- 1) Proportion of participants with clinical response (defined as a $\geq 50\%$ reduction in MADRS score from baseline).
- 2) Proportion of participants with remission (defined as a MADRS score of ≤ 12 on day 14).

26c. Other exploratory secondary outcomes

- 1) MADRS scores at postoperative Days 5, 7, and 14
- 2) Hospital Anxiety and Depression Scale
- 3) Cumulative inpatient opioid use
- 4) Hospital length of stay
- 5) Average inpatient opioid use per day
- 6) Opioid use at postop day 7
- 7) Opioid use at postop day 14
- 8) Postoperative numeric pain scores
- 9) Postoperative pain interference scores

27. Analysis methods

27a. Analysis of the primary outcome

